8.1.4. Other Endpoints of Interest

8.2. Analysis Conventions

If not otherwise specified, subjects will be analyzed according to the Part (and Cohort, for Part A) they enrolled into. In addition, for Part A, overall summary of Cohort 1 and Cohort 2 combined will also be provided. No combined summary of Part A and Part B will be provided.

- **Part A, Cohort 1:** Moderate ($30 \text{ mL/min} \leq \text{eGFR}_{\text{CG}} \leq 59 \text{ mL/min}$) or severe ($15 \text{ mL/min} \leq \text{eGFR}_{\text{CG}} < 30 \text{ mL/min}$) renal impairment
- **Part A, Cohort 2:** ESRD ($\text{eGFR} < 15 \text{ mL/min}$) maintained on HD
- **Part B:** Moderate (CPT Class B [[Appendix 7](#)]; Score of 7-9 inclusive) or Severe (CPT Class C; Score of 10-12 inclusive) hepatic impairment

8.2.1. Analysis Sets

8.2.1.1. Efficacy

The primary analysis set for efficacy analysis is the Full Analysis Set (FAS), defined as all subjects who are enrolled and received at least one dose of study drug.

8.2.1.2. Safety

The primary analysis set for safety analyses is the Safety Analysis Set, defined as all subjects who are enrolled and received at least one dose of study drug.

All data collected during treatment will be included in the safety summaries.

8.2.1.3. Pharmacokinetics

The PK analysis set will include all subjects who have received at least one dose of study medication and for whom concentration data of any analytes of interest are available. The PK analysis set will be used for analyses of concentration data.

8.2.1.4. Biomarkers

The Biomarker analysis set will include all subjects who have evaluable biomarkers data.

8.2.1.5. DEXA

8.2.1.5.1. Hip DXA Analysis Set

The Hip DXA Analysis Set includes all subjects who were randomized and had received at least 1 dose of study drug, and had nonmissing baseline hip BMD values.

8.2.1.5.2. Spine DXA Analysis Set

The Spine DXA Analysis Set includes all subjects who were randomized and had received at least 1 dose of study drug, and had nonmissing baseline spine BMD values.

8.3. Data Handling Conventions

For categorical efficacy endpoints, missing data will be handled using a M = F approach. Sensitivity analyses will be performed using a missing = excluded (M=E) approach.

For secondary safety endpoints of change from baseline in eGFR_{CG} and percent change from baseline in hip and spine bone mineral density (BMD), an analysis will be performed using the last observation carried forward (LOCF) method to impute missing data.

For the remaining endpoints, values for missing data will not be imputed, unless specified otherwise.

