The co-primary endpoints of GS-US-174-0108 were proportion with tolerability failure (adverse event [AE] resulting in permanent study drug discontinuation), and confirmed renal event (an increase from baseline in serum creatinine [sCr] of ≥ 0.5 mg/dL or decrease in serum phosphate [PO₄] below 2.0 mg/dL). At Week 48, rates of tolerability failure were comparable across treatment groups (TDF 6.7%, FTC/TDF 4.4%, ETV 9.1%). Confirmed increases in sCr or decreases in PO₄ occurred in a similar percentage of patients in the TDF and FTC/TDF groups (8.9% and 6.7%, respectively); however, confirmed renal events occurred in a lower percentage of ETV-treated patients (4.5%). The percentages of patients with AEs and SAEs considered related to study drug, and AEs resulting in permanent study drug discontinuation, or treatment emergent deaths (2 subjects in each group), were low and similar between treatment groups.

Although the study was not sufficiently powered to assess antiviral efficacy, the proportions of patients (95% confidence interval) in GS-US-174-0108 achieving HBV DNA < 69 IU/mL (< 400 copies/mL) at Week 48 were comparable between treatment groups (TDF 70% [57%, 84%], FTC/TDF 88% [78%, 98%], ETV 73% [54%, 91%] when evaluated by non-completers or switch equals failure [NC/S=F]), as were the rates of ALT normalization (TDF 46% [27%, 65%], FTC/TDF 64% [45%, 83%], ETV 41% [18%, 65%] [NC/S=F]). No patient in any treatment group developed resistance to study drug, and similar percentages of patients in each group showed improvements in CPT and model for end-stage liver disease (MELD) scores at Week 48 {Liaw 2011}.

When patients in GS-US-174-0108 were followed longer-term, a total of 69/112 (62%) patients completed 168 weeks of double-blind therapy with 12 (6-TDF, 3-FTC/TDF, and 3-ETV) patients switching to open-label FTC/TDF (10 patients prior to Week 48), and 11 (3-TDF, 7-FTC/TDF, 1-ETV) patients receiving OLT (8 of 11 patients completed the study through 168 weeks). In general, the safety and efficacy of TDF, FTC/TDF, and ETV were comparable and maintained through Week 168. No TDF resistance was documented over the entire (168 weeks) duration of treatment.

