8.1.3. Secondary Endpoint

[figure not shown]
The Secondary safety endpoints are:

[figure not shown]
- Incidence of graded adverse events and graded laboratory abnormalities at Week 48 and 96
- Change from baseline in eGFR_{CG} at Weeks 24, 48, and 96 in subjects with moderate or severe renal impairment and hepatically impaired subjects
- Percent change from baseline in hip and spine bone mineral density (BMD) at Weeks 24, 48, and 96

The Secondary efficacy endpoints are:

- Proportion of subjects achieving virologic response (plasma HBV DNA < 20 IU/mL) at Weeks 48 and 96
- Proportion of subjects with plasma HBV DNA < 20 IU/mL and target detected/not detected (i.e. < LLOD) at Weeks 24, 48, and 96
- Proportion of subjects with serological response (loss of HBsAg and seroconversion to anti-HBs, loss of HBeAg and seroconversion to anti-HBe in HBeAg-positive subjects) at Weeks 24, 48, and 96
- Proportion of subjects with biochemical response (normal ALT and normalized ALT) at Weeks 24, 48, and 96
- Change in fibrosis as assessed by FibroTest[®] at Weeks 24, 48, and 96
- Change from baseline in CPT score ([Appendix 7](#)) and MELD score at Weeks 24, 48, and 96 in hepatically impaired subjects

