8.5.2. Secondary Analyses

Continuous secondary endpoints will be summarized using conventional descriptive statistics (n, mean, standard deviation, median, Q1, Q3, minimum, and maximum).

Categorical secondary endpoints will be summarized by number and percentage of subjects that meet the endpoint. Missing data will be handled by the M = F approach. Sensitivity analyses will be performed for the primary endpoint using M = E approach.

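### CPT and MELD change in Part B is summarised without imputation and without any stated rule for death or liver transplant, so the observed summary may be biased towards improvement

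*Protocol*

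**What the plan says.** Protocol section 8.1.3 lists "Change from baseline in CPT score", together with MELD, at Weeks 24, 48 and 96 in hepatically impaired subjects as a secondary efficacy endpoint. Section 8.5.2 sets the method: "Continuous secondary endpoints will be summarized using conventional descriptive statistics (n, mean, standard deviation, median, Q1, Q3, minimum, and maximum").

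Section 8.3 has three rules for missing data:

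- Categorical efficacy endpoints: "For categorical efficacy endpoints, missing data will be handled using a M = F approach".
- Change in eGFR by Cockcroft-Gault and percent change in hip and spine BMD: "an analysis will be performed using the last observation carried forward (LOCF) method to impute missing data".
- Everything else: "For the remaining endpoints, values for missing data will not be imputed, unless specified otherwise".

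CPT and MELD change is continuous and is not on the LOCF list, so the third rule applies. The supplied SAP text covers COVID-19 disruption, the Week 96 window, last dose date and the creatinine correction. It says nothing about CPT or MELD. Its sections 2 and 3 refer to a main SAP (Tables 3-2 to 3-8 and Section 3.8.1) that is not among the documents.

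On transplant, section 4.3 excludes prior recipients at entry. Section 6.6 does not list transplant as a reason to stop study drug. Section 6.5 asks sites to keep subjects who stop drug in the study, and collects CPT and MELD from Part B subjects at the Early Discontinuation visit.

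**The concern.** Death from liver failure and liver transplant are the worst hepatic outcomes a Part B subject can have, and both affect whether a later score exists and what it means. After death there is no score, so the subject leaves the Week 48 or Week 96 summary. After transplant a score may still be recorded, but it describes a different liver and could count as an improvement. If lost subjects would have done worse than those still measured, the observed mean is more favourable than the mean over everyone who started.

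The protocol's own background made this foreseeable. Section 1.2.4.3 describes the earlier TDF study in decompensated disease, where transplanted patients could continue but were censored at transplant for secondary efficacy. This protocol carries over no such rule. At stake is how a reader interprets a table that will be taken as evidence on liver function after the switch.

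**Working it through.** The plan has no figure of its own to reproduce. Section 8.9 states that no formal sample size calculation was done, and no expected CPT change, SD or dropout rate is given.

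**Inputs.** Part B has about 30 subjects (section 3.1). From section 1.2.4.3, the earlier study had 112 patients in three groups, with "treatment emergent deaths (2 subjects in each group"), which makes 6 deaths. These are reported alongside the Week 48 results, so Week 48 is assumed as their timing. It also had "11 (3-TDF, 7-FTC/TDF, 1-ETV) patients receiving OLT" over 168 weeks, and 8 of those 11 completed the study.

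**Expected events, assuming constant rates and no overlap of death and transplant.**

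Probability of an event by week *t* = 1 - (1 - 6/112)^(*t*/48) × (1 - 11/112)^(*t*/168)

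| Week | Probability | Expected among 30 |
|---|---|---|
| 24 | 4.1% | 1.2 |
| 48 | 8.1% | 2.4 |
| 96 | 15.6% | 4.7 |

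That study required HBV DNA of at least 10^3 copies/mL. Part B subjects are suppressed, and section 4.2 admits a past CPT score of 7 or more with any current score up to 12. Lower rates are therefore plausible, and 0 to 5 events by Week 96 is a judged range. The binomial chance of at least 3 events among 30 is 86% at a 15.5% event rate, 59% at 10% and 19% at 5%.

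**Effect on the mean CPT change.** Let *s* be the observed mean, *k* the number lost and *w* the change each lost subject would have had. Both *s* and *w* are assumed.

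All-subject mean = [(30 - *k*) × *s* + *k* × *w*] / 30

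With *s* = -0.3 and *w* = 3:

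- *k* = 2: (28 × -0.3 + 2 × 3)/30 = -0.08
- *k* = 3: (27 × -0.3 + 3 × 3)/30 = +0.03
- *k* = 5: (25 × -0.3 + 5 × 3)/30 = +0.25

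Each lost subject moves the mean by (3 + 0.3)/30 = 0.11 point. The number of losses at which the sign changes depends on the assumptions:

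| *s* | *w* | First *k* with all-subject mean above 0 |
|---|---|---|
| -0.3 | 3 | 3 |
| -0.3 | 2 | 4 |
| -0.3 | 1 | 7 |
| -0.5 | 3 | 5 |

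The documents give nothing from which to do the same for MELD. The mechanism is identical.

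**The case against.** The strongest objection is that the governing SAP is not in hand. The no-imputation clause allows for exceptions, and the main SAP may define shift categories or a rule for death. This stands, and it makes the request conditional.

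Second, the study is exploratory, uncontrolled and descriptive, and no test or decision rests on this mean. Deaths are serious adverse events and will be reported by Part. The planned summary gives n at each visit, so attrition will show. The Early Discontinuation visit can record deterioration in subjects who stop drug alive. All true, and it limits the severity. But n alone does not say why subjects are missing, safety tables do not correct the score summary, and no visit records a score after death.

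Third, a reader might infer that transplanted subjects drop out. The documents do not say so. Equally, the entry of new-liver scores is only a possibility: section 5.3 excludes immunosuppressants, including tacrolimus and cyclosporine, and section 6.4.3 gives treatment-free follow-up visits for Part A only. The plan leaves either route open.

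Fourth, one could treat CPT and MELD as the only view of hepatic function, in the group with the highest mortality. Neither is supported. Liver function tests are taken at every visit, graded bilirubin, albumin and INR abnormalities feed the primary safety endpoint, and no mortality figure is given for the haemodialysis cohort.

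**Conclusion.** The gap is real on the supplied text: CPT and MELD change is an observed-case summary, and neither death nor transplant has a stated rule. The supportable conclusion is that this summary may be biased towards improvement. It does not follow that the mean will show improvement. If the subjects still measured worsen on average by 0.3 point, the observed mean shows worsening.

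The size is uncertain. With 0 to 5 events among 30, the shift in mean CPT change runs from nothing to 5 × 0.11 = 0.55 point when *s* = -0.3 and *w* = 3, and the sign changes at 3 events. A reader might infer that two events are enough. That requires scoring each event at the CPT maximum of 15 from a baseline of 8, with survivors improving by 0.5: (28 × -0.5 + 2 × 7)/30 = 0.0. With a 3-point worsening instead, two events leave the mean at -0.27.

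These figures rest on event rates from a viraemic population, an inferred time for its deaths, no overlap between death and transplant, and assumed score changes. The point is a cheap improvement to a descriptive secondary endpoint.

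**What to change.** First check the main SAP. If it has no rule, state the following in sections 8.3 and 8.5.2:

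1. At Weeks 24, 48 and 96, CPT and MELD are also tabulated over all Part B Full Analysis Set subjects as improved, unchanged, worsened, died, transplanted or otherwise missing.
2. Scores taken after liver transplant are left out of the change-from-baseline summary.
3. The planned observed-case 8-number summary is kept beside this table.
4. Optionally, a sensitivity analysis gives the median and quartiles with death and transplant ranked worst.

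The table matters most. In the ranked version, *k* events move the median by only *k*/2 rank positions, from rank (31 - *k*)/2 among those observed to rank 15.5 among 30. Extending LOCF would not help, because it would carry forward a score from before the event.

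The cost is SAP wording and one more table, with no change to visits, samples or clinical management. The ranked version mixes death with score change, so its components should be shown separately. If any of this is added after the Week 24 analysis, it should be labelled as such.

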8.4. Demographic Data and Baseline Characteristics

Demographic and baseline measurements will be summarized using standard descriptive methods.

Demographic summaries will include sex, race/ethnicity, age, etc.

Baseline data will include a summary of body weight, height, body mass index (BMI), HBV DNA level, years positive for HBV, ALT level (\leq ULN, $>$ ULN), previous TDF use and other oral nucleoside/nucleotide treatment experience, previous interferon experience, fibrotest score, CPT and MELD score, and HBV genotype by history, if available.

8.5. Efficacy Analysis

8.5.1. Primary Analysis

The primary analysis will be performed when the last subject has completed Week 24 assessments or discontinued prematurely.

The proportion of subjects with plasma HBV DNA $<$ 20 IU/mL will be summarized descriptively using an M = F approach.

8.5.2. Secondary Analyses

Continuous secondary endpoints will be summarized using conventional descriptive statistics (n, mean, standard deviation, median, Q1, Q3, minimum, and maximum).

Categorical secondary endpoints will be summarized by number and percentage of subjects that meet the endpoint. Missing data will be handled by the M = F approach. Sensitivity analyses will be performed for the primary endpoint using M = E approach.

8.6. Safety Analysis

All safety data collected on or after the date that IMP was first dispensed up to the end of treatment will be summarized. Data for the pretreatment will be included in data listings.

8.6.1. Primary Safety Analysis

Incidence of graded adverse events and graded laboratory abnormalities will be summarized. For more details, please refer to Sections 8.6.3 and 8.6.4 below.

8.6.2. Secondary Safety Analysis

The change from baseline in eGFR_{CG} at Weeks 24, 48, and 96 in subjects with moderate or severe renal impairment will be summarized.

The percent change from baseline in hip and spine BMD at Weeks 24, 48, and 96 will be summarized.

8.6.3. Extent of Exposure

A subject's extent of exposure to IMP data will be generated from the IMP administration data. Exposure data will be summarized.

8.6.4. Adverse Events

Clinical and laboratory adverse events will be coded using the Medical Dictionary for Regulatory Activities (MedDRA). System Organ Class (SOC), High-Level Group Term (HLGT), High-Level Term (HLT), Preferred Term (PT), and Lower-Level Term (LLT) will be attached to the clinical database.

Events will be summarized on the basis of the date of onset for the event. A treatment-emergent adverse event will be defined as any adverse event that begins on or after the date of first dose of IMP up to the date of last dose of IMP. Continuing adverse events diagnosed prior to the start of treatment and worsening in severity grade, or non-serious adverse events at baseline which become serious, or adverse events resulting in treatment discontinuation after the start of treatment will also be considered treatment-emergent. Summaries (number and percentage of subjects) of treatment-emergent adverse events (by SOC and PT) will be provided:

- Treatment-emergent adverse events
- Treatment-emergent study drug-related adverse events

- Grade 3 or 4 treatment-emergent adverse event
- Grade 3 or 4 treatment-emergent study drug-related adverse event
- Grade 2, 3, or 4 treatment-emergent adverse event
- Grade 2, 3, or 4 treatment-emergent study drug-related adverse event
- AE that caused permanent discontinuation from study drug
- AE that caused change in dose or temporary interruption of study drug
- Treatment-emergent serious adverse event
- Treatment-emergent study drug-related serious adverse event

8.6.5. Laboratory Evaluations

Selected laboratory data (using conventional units) will be summarized using only observed data. Data and change from baseline at all scheduled time points will be summarized.

Graded laboratory abnormalities will be defined using the grading scheme in [Appendix 4](#).

Incidence of treatment-emergent laboratory abnormalities, defined as values that increase at least one toxicity grade from baseline at any time post baseline up to the end of treatment will be summarized.

Laboratory abnormalities that occur before the first dose of IMP or after the subject has been discontinued from treatment will be included in a data listing.

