Change from baseline in serum creatinine was the third key alpha-controlled safety endpoint. Overall, increases from baseline in mean values for serum creatinine were smaller in the TAF group compared with the TDF group. Mean (SD) changes from baseline at Week 48 were 0.010 (0.1140) mg/dL for the TAF group and 0.024 (0.0974) mg/dL for the TDF group ($p = 0.012$). Graded serum creatinine abnormalities were reported for 6 subjects (0.7%) in the TAF group; all of which were Grade 1 or 2. Of the 6 subjects, 5 subjects had isolated serum creatinine elevations that were not associated with decreased eGFR. One subject, who had a relevant medical history of hypertension and diabetes, had multiple instances of graded creatinine elevations and $eGFR \leq 50$ mL/min. No subjects in the TDF group had graded serum creatinine elevations.

In the TAF group, decreases from baseline in median $eGFR_{CG}$ values were significantly smaller compared with the TDF group. Median (Q1, Q3) changes from baseline at Week 48 were -1.2 ($-8.4, 7.5$) mL/min in the TAF group and -5.4 ($-12.0, 3.0$) mL/min in the TDF group ($p < 0.001$). The overall number of subjects who had any confirmed renal laboratory abnormality (ie, confirmed increases from baseline in creatinine of at least 0.5 mg/dL, or $eGFR_{CG}$ below 50 mL/min, or confirmed phosphorus < 2 mg/dL, was small (TAF 0.6%, 5 subjects; TDF 1.6%, 7 subjects). Most instances were isolated, transient, and resolved without treatment.

Summary of Proteinuria by Urinalysis (Dipstick) and by Quantitative Assessment

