7.5.6. Management of Potential Nephrotoxicity

For subjects with moderate or severe renal impairment (Part A, Cohort 1), and subjects with hepatic impairment (Part B), eGFR_{CG} will be followed post-baseline during the study.

eGFR_{CG} is calculated by:

$$\frac{(140 - \text{age in years}) (\text{actual body weight [kg]})}{(72) (\text{serum creatinine [mg/dL]})}$$

(Note: multiply estimated rate by 0.85 for women)

Any subject with a post baseline eGFR_{CG} < 15 mL/min must have serum creatinine measured again within 3 calendar days of receipt of results. At the time of this repeat serum creatinine assessment, serum Cystatin C will also be measured and the eGFR by CKD-EPI (cystatin C) will be calculated and compared with the baseline measurement. Any subject who has an eGFR_{CG} < 15 mL/min who also experiences > 20% reduction in eGFR by CKD-EPI (cystatin C) from baseline or any subject who has other clinical and/or laboratory evidence of acute renal failure will be discussed with the Medical Monitor and may require discontinuation from study drugs.

CKD-EPI (cystatin C) formula adjusted for age and sex:

$$\text{eGFR (mL/min/1.73m}^2\text{)} = 133 \times \min(\text{Scys}/0.8, 1)^{-0.499} \times \max(\text{Scys}/0.8, 1)^{-1.328} \times 0.996^{\text{Age}}$$

[× 0.932 if female],

where Scys is serum cystatin C (mg/L), min (Scys/0.8,1) indicates the minimum of Scys/0.8 or 1, and max (Scys/0.8,1) indicates the maximum of Scys/0.8 or 1.

If the eGFR_{CG} is confirmed to be < 15 ml/min and hemodialysis is to be initiated, the subject can remain on study after discussion with the Medical Monitor. However, any subject with eGFR < 15 mL/min who does not initiate hemodialysis, or those who initiate other forms of renal support (e.g. peritoneal dialysis) will be required to permanently discontinue study drug.

All subjects with moderate or severe renal impairment with a change from baseline serum creatinine of ≥ 0.4 mg/dL must have serum creatinine repeated, with a concurrent urinalysis and urine chemistry, within 2 weeks of receipt of results. If a subject has a confirmed change from baseline serum creatinine of ≥ 0.4 mg/dL, the Medical Monitor should be notified and a consultation with a nephrologist should be obtained.

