8.1.2. Primary Endpoint

- The primary safety endpoint is the incidence of graded adverse events and graded laboratory abnormalities at Week 24.
- The primary efficacy endpoint is the proportion of subjects achieving virologic response (plasma HBV DNA < 20 IU/mL) at Week 24.

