Blood Urea Nitrogen	1.25 to 2.50 × ULN	> 2.50 to 5.00 × ULN	> 5.00 to 10.00 × ULN	> 10.00 × ULN
Hyperuricemia	>ULN to 10.0 mg/dL >ULN to 597 μmol/L	> 10.0 to 12.0 mg/dL > 597 to 716 μmol/L	> 12.0 to 15.0 mg/dL > 716 to 895 μmol/L	> 15.0 mg/dL > 895 μmol/L
Hypouricemia Adult and Pediatric ≥ 1 year	1.5 mg/dL to < LLN 87 μmol/L to < LLN N/A	1.0 to < 1.5 mg/dL 57 to < 87 μmol/L 1.0 mg/dl to <LLN- 57 μmol to <LLN	0.5 to < 1.0 mg/dL 27 to < 57 μmol/L 0.5 to < 1.0 mg/dL 27 to < 57 μmol/L	< 0.5 mg/dL < 27 μmol/L < 0.5 mg/dL < 27 μmol/L
Infant < 1 Year				

CHEMISTRY				
	Grade 1	Grade 2	Grade 3	Grade 4
Creatinine**	> 1.50 to 2.00 mg/dL > 133 to 177 µmol/L	> 2.00 to 3.00 mg/dL > 177 to 265 µmol/L	> 3.00 to 6.00 mg/dL > 265 to 530 µmol/L	> 6.00 mg/dL > 530 µmol/L
Bicarbonate Adult and Pediatric ≥ 4 Years	16.0 mEq/L to < LLN 16.0 mmol/L to < LLN	11.0 to < 16.0 mEq/L 11.0 to < 16.0 mmol/L	8.0 to < 11.0 mEq/L 8.0 to < 11.0 mmol/L	< 8.0 mEq/L < 8.0 mmol/L
Pediatric < 4 Years	NA	11.0 mEq/L to <LLN 11.0 mmol/L to <LLN	8.0 to < 11.0 mEq/L 8.0 to < 11.0 mmol/L	< 8.0 mEq/L < 8.0 mmol/L
Triglycerides (Fasting)	NA	500 to 750 mg/dL 5.64–8.47 mmol/L	> 750 to 1200 mg/dL > 8.47–13.55 mmol/L	> 1200 mg/dL > 13.55 mmol/L
LDL (Fasting) Adult	130 to 160 mg/dL 3.35 to 4.15 mmol/L	>160 to 190 mg/dL >4.15 to 4.92 mmol/L	> 190 mg/dL >4.92 mmol/L	NA
LDL (Fasting) Pediatric >2 to <18 years	110 to 130 mg/dL 2.84 to 3.37 mmol/L	>130 to 190 mg/dL >3.37 to 4.92 mmol/L	> 190 mg/dL >4.92 mmol/L	NA
Hypercholesterolemia (Fasting)	200 to 239 mg/dL 5.16 to 6.19 mmol/L	> 239 to 300 mg/dL > 6.19 to 7.77 mmol/L	> 300 mg/dL > 7.77 mmol/L	NA
Pediatric < 18 Years	170 to 199 mg/dL 4.39 to 5.15 mmol/L	> 199 to 300 mg/dL > 5.15 to 7.77 mmol/L	> 300 mg/dL > 7.77 mmol/L	NA
Creatine Kinase	3.0 to < 6.0 × ULN	6.0 to < 10.0 × ULN	10.0 to < 20.0 × ULN	≥ 20.0 × ULN

* Calcium should be corrected for albumin if albumin is < 4.0 g/dL

** An overlap between the Grade 1 scale and the Lab's normal range for creatinine may result for Male subjects >70 yrs. Please follow the Gilead convention of grading any result within the LLN and ULN a 0.

ENZYMES				
	Grade 1	Grade 2	Grade 3	Grade 4
AST (SGOT)	1.25 to 2.50 × ULN	> 2.50 to 5.00 × ULN	> 5.00 to 10.00 × ULN	> 10.00 × ULN
ALT (SGPT)	1.25 to 2.50 × ULN	> 2.50 to 5.00 × ULN	> 5.00 to 10.00 × ULN	> 10.00 × ULN
GGT	1.25 to 2.50 × ULN	> 2.50 to 5.00 × ULN	> 5.00 to 10.00 × ULN	> 10.00 × ULN

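### In the primary safety endpoint, creatinine counts only through a shift in an absolute grade, so within-band rises are missed and no count of baseline-relative rises is planned

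*Protocol*

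**What the plan says.** Protocol 8.1.2 states: "The primary safety endpoint is the incidence of graded adverse events and graded laboratory abnormalities at Week 24". Section 8.6.5 adds that "Graded laboratory abnormalities will be defined using the grading scheme in" Appendix 4, and counts treatment-emergent abnormalities as those "defined as values that increase at least one toxicity grade from baseline at any time post baseline". Section 8.6.1, which introduces the primary safety analysis, points to 8.6.3 and 8.6.4 (exposure and adverse events). Even so, 8.6.5 holds the only laboratory counting rule in the supplied documents, so I take it as the rule for the laboratory part of the endpoint.

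In Appendix 4, creatinine Grade 1 is "> 1.50 to 2.00 mg/dL", Grade 2 is above 2.00 to 3.00, Grade 3 is "> 3.00 to 6.00 mg/dL" and Grade 4 is above 6.00 mg/dL. There is no criterion relative to baseline. Hemoglobin in the same appendix has one for HIV-negative subjects. Appendix 4 has no grade for eGFR.

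Renal function is also covered elsewhere:
- Change in eGFR_CG is a secondary safety endpoint for Cohort 1 and Part B (8.1.3).
- Change in serum creatinine is summarized descriptively (Synopsis, Statistical Methods; also 8.6.5 for selected laboratory data).
- A laboratory abnormality that needs intervention or changes study drug must be recorded as an adverse event (7.1.3).
- In 7.5.6, subjects with moderate or severe renal impairment "with a change from baseline serum creatinine of ≥ 0.4 mg/dL must have serum creatinine repeated". This is a management trigger; no incidence of it is planned.

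**The concern.** Part A is selected for impaired kidneys, and the kidney is an organ of particular interest in a switch from TDF. A count based on absolute bands registers where a subject sits relative to a cut-point rather than how far that subject has declined. A large rise inside a wide band is not counted, while a trivial rise across a cut-point is.

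The protocol's own background shows that the two kinds of count can disagree. In the Phase 3 studies (Section 1.2.3, renal laboratory parameters), graded creatinine abnormalities occurred in 6 TAF subjects and no TDF subjects, and 5 of the 6 had no associated fall in eGFR. The confirmed renal measure, which included "confirmed increases from baseline in creatinine of at least 0.5 mg/dL" together with eGFR_CG and phosphorus criteria, ran the other way: 5 TAF subjects (0.6%) against 7 TDF subjects (1.6%). That measure is a composite, so the comparison is only indicative.

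What is at stake is how the Week 24 safety result can be read. Means and medians of change do not say how many subjects declined, and the grade-shift table answers that question poorly for creatinine.

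**Working it through.** The plan gives no figure to reproduce: it has no sample-size calculation (8.9) and no baseline creatinine distribution.

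**Inputs.** The creatinine cut-points are 1.50, 2.00, 3.00 and 6.00 mg/dL (Appendix 4). The Cockcroft-Gault formula is (140 − age) × weight / (72 × creatinine), times 0.85 for women (Section 3.1). Cohort 1 has eGFR_CG of 15 to 59 mL/min.

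**1. Largest uncounted fall within a band.** At fixed age and weight, eGFR_CG is proportional to 1/creatinine, so the largest fall without a grade shift is 1 − lower limit/upper limit.

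| Baseline grade | Band (mg/dL) | Largest uncounted fall |
|---|---|---|
| 1 | 1.50 to 2.00 | 1 − 1.50/2.00 = 25% |
| 2 | 2.00 to 3.00 | 1 − 2.00/3.00 = 33% |
| 3 | 3.00 to 6.00 | 1 − 3.00/6.00 = 50% |
| 4 | above 6.00 | no limit |

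Grade 0 is affected too: 1.00 to 1.50 is a 33% fall, and 0.80 to 1.50 is 1 − 0.80/1.50 = 47%.

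**2. One illustrative man (assumed 65 years, 70 kg).** The constant is 75 × 70/72 = 72.9.
- Creatinine at eGFR_CG 59, 30 and 15 is 72.9/59 = 1.24, 72.9/30 = 2.43 and 72.9/15 = 4.86 mg/dL. He would start at Grade 0 for eGFR_CG above 72.9/1.50 = 48.6.
- A rise from 3.05 to 4.80 mg/dL takes eGFR_CG from 23.9 to 15.2, a fall of 1 − 3.05/4.80 = 36%. There is no grade shift, and eGFR_CG stays above 15.
- A rise from 2.98 to 3.01 mg/dL is a fall of 1 − 2.98/3.01 = 1%, and it counts.

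**3. A rise of exactly 0.4 mg/dL** gives no grade shift when baseline is up to 1.10, above 1.50 to 1.60, above 2.00 to 2.60, above 3.00 to 5.60, or above 6.00 mg/dL.

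**4. How many subjects this could affect.** Age, weight, sex and severity mix are not in the documents, so I assumed 36 scenarios: mean age 55, 65 or 72 (SD 10); mean weight 60 or 70 kg (men +4, women −6, SD 10); 70% men; 10%, 25% or 40% of Cohort 1 severe; and eGFR uniform or skewed to the milder end. ESRD eGFR was assumed uniform from 5 to 15.

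| Change from baseline, Cohort 1 | Share with no grade shift |
|---|---|
| eGFR_CG down 20% | 42% to 64% |
| eGFR_CG down 25% | 25% to 51% |
| eGFR_CG down 30% | 16% to 41% |
| eGFR_CG down 40% | 5% to 23% |
| eGFR_CG down 50% | 0.4% to 10% |
| creatinine up 0.4 mg/dL | about 39% to 58% |

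The share graded at baseline is 14% to 72% of moderate subjects, 22% to 83% of Cohort 1 (below half in 12 of 36 scenarios) and 37% to 87% of Part A. In ESRD, 42% to 78% start at Grade 4.

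**The case against.** A reader might infer that most of this population starts graded and that large renal declines are never counted. The documents do not support that.

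- **Starting grade.** No baseline creatinine is given, and many moderate subjects would start at Grade 0. The missed rises come from the width of the bands, and Grade 0 subjects are missed as well.
- **Large declines.** In the assumed scenarios, most Cohort 1 falls of 40% or more do shift a grade. The largest within-band rises can also enter by another route. For the illustrative man, 3.05 to 5.95 mg/dL takes eGFR_CG from 23.9 to 12.3. If that is confirmed, 7.5.6 leads to hemodialysis or permanent discontinuation of study drug, and 7.1.3 then requires an adverse event. Graded adverse events belong to the same primary endpoint. Creatinine and eGFR_CG changes are summarized besides.
- **The Grade 4 ceiling.** It falls mainly on dialysis subjects, in whom the plan does not follow eGFR_CG. A reader might also infer that these subjects dilute a percentage, but 8.6.5 states no denominator.
- **A fixed threshold has its own scale problem.** A rise of 0.4 mg/dL is a 24% fall from 1.24 mg/dL (0.4/1.64) but 7.6% from 4.86 (0.4/5.26). Eligibility accepts a creatinine difference of up to 25% of the screening value as stable, which is 0.61 mg/dL at 2.43 and 1.2 at 4.86.
- **Status of the study.** It is exploratory and descriptive, and no decision rule depends on this count. The supplied SAP document is an addendum to a main SAP that was not available.

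All of these points stand as limits. They do not remove the gap: a rise such as 3.05 to 4.80 mg/dL shifts no grade, need not become an adverse event, and is visible only inside a descriptive summary.

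**Conclusion.** The point holds in a limited form. Within the laboratory part of the primary safety endpoint, creatinine counts only through a shift of at least one absolute grade. Falls in eGFR_CG of up to 25%, 33% or 50% within Grades 1, 2 or 3 can go uncounted there, and a subject at Grade 4 at baseline cannot be counted at all. These limits are exact at fixed age and weight. The shares of Cohort 1 affected rest on assumed distributions and are ranges, not estimates for the enrolled subjects.

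The supplied documents plan no number or percentage of subjects with a baseline-relative creatinine rise. If the main SAP contains such a table, the point is met. Because the study is descriptive and the data already exist for most of what is needed, this is a worthwhile improvement and does not invalidate the endpoint.

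**What to change.** In Protocol 8.6.5 (and the SAP), keep the grade-shift table and add beside the primary safety summary at Week 24, and again at Weeks 48 and 96, the number and percentage of:

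- Cohort 1 subjects with a confirmed creatinine rise from baseline of at least 0.4 mg/dL, using the repeat test that 7.5.6 already requires;
- Cohort 1 and Part B subjects with a rise of at least 0.5 mg/dL at two consecutive post-baseline measurements. This threshold appears in the Phase 3 summary (1.2.3) and in the co-primary renal event of the decompensated-liver study (1.2.4.3).

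The 0.4 mg/dL count is limited to Cohort 1 because the trigger in 7.5.6 does not cover Part B. Both counts should use the corrected creatinine values defined in SAP Section 4. For Cohort 2, show the creatinine grade shift separately, with the number already at Grade 4 at baseline, and do not read it as a measure of renal decline.

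The cost is one extra table. More renal events may be reported, including small relative changes in subjects with high baseline creatinine, so baseline creatinine should be shown alongside. No management rule changes.
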